8.11.2.3. Dose Reduction

In the event of Grade 3 treatment-related AEs, the participant may continue on study if there is evidence of clinical benefit as judged by the treating physician, but could do so at a reduced dose of futuximab/modotuximab once retreatment criteria are met ([Section 6.1.5](#)) (specific instructions for dose reduction linked to IRR, dermatologic AEs, and hypomagnesemia, are provided in Appendices 9, 10 and 11, respectively). All dose reductions of futuximab/modotuximab must be documented on the appropriate page of the participant's e-CRF.

If toxicity is to be managed by dose reduction, the futuximab/modotuximab dose will be decreased as shown in ([Table \(8.11.2.3\) 1](#)). Dose reduction may occur either during treatment cycles, or between cycles, as clinically indicated.

Table (8.11.2.3) 1 - Dose reduction of futuximab/modotuximab

Starting dose (Dose level 0)	Dose level -1	Dose level -2
Futuximab/modotuximab*	6 mg/kg	4.5 mg/kg

*Note: Dose Reductions for 9 mg/kg loading dose not applicable. The number of dose reductions allowed is limited to 2

Abbreviations (in alphabetical order): kg, kilogram; mg, milligram

A maximum of 2 dose reductions for futuximab/modotuximab-related toxicity are allowed (to a minimum dose of 3 mg/kg). Do not re-escalate dose after it has been reduced.

8.12. Recommendations regarding treatment of toxicities

8.12.1. Management of nausea and vomiting

Trifluridine/tipiracil has emetogenic potential.

- A single antiemetic agent, such as dexamethasone, a 5-HT₃ receptor antagonist or a dopamine receptor antagonist, such as metoclopramide may be considered for prophylaxis.
- If a participant experiences acute or delayed nausea or vomiting due to trifluridine/tipiracil, it is advised that, at the next cycle, a higher antiemetic regimen may be given.
- In case a participant experiences of anticipatory nausea and vomiting, benzodiazepines are recommended. The above is based on Multinational Association of Supportive Care in Cancer (MASCC) and European Society for Medical Oncology (ESMO) guidelines³⁶ and Hesketh *et al.* (2016).³⁷

8.12.2. Management of diarrhoea

Educate both participants and participants' families regarding the potential seriousness of chemotherapy-induced diarrhoea. Instruct participants to immediately contact the study site

staff at the first sign of loose stool. The participant should be instructed to record the number of stools and report symptoms indicating a complicated diarrhoea (see list below).

- Educate the participant regarding the dietary measures to be taken in case of diarrhoea.
- Provide participants with loperamide (or other standard antidiarrheal therapy) and instruct the participant on how to use it at the first sign of diarrhoea.
- Monitor the participant's fluid and electrolyte balance, with appropriate intervention as clinically indicated with fluids and electrolyte replacement ³⁸

Mild to moderate diarrhoea (Grade 1 or 2 according to NCI-CTCAE without complications):

- It is recommended to start dietary modifications and standard antidiarrheal therapy for example loperamide at an initial dose of 4 mg followed by 2 mg every 4 hours or after every unformed stool (not to exceed 16 mg/day).
- If diarrhoea resolves with antidiarrheal therapy, the dietary modifications should be continued (with a gradually addition of solid foods). Antidiarrheal therapy may be discontinued when the participant has been diarrhoea-free for at least 12 hours.
- If diarrhoea persists for more than 24 hours, the dose of antidiarrheal therapy should be increased (for loperamide increase to 2 mg every 2 hours), and oral antibiotics may be started as prophylaxis for infection.
- If diarrhoea has not resolved after 48 hours on initial treatment, the participant should be started on a second-line antidiarrheal agent.

Complicated diarrhoea:

- Any Grade 3 or 4 diarrhoea is classified as "complicated". In addition, Grade 1 or 2 diarrhoea and at least one of the following symptoms are also considered as complicated:
 - Fever, sepsis, moderate to severe cramping.
 - Grade 2 nausea/vomiting.
 - Decreased performance status.
 - Neutropenia.
 - Frank bleeding.
 - Dehydration.
- Aggressive management of complicated cases should involve:
 - Intravenous (IV) fluids.
 - Octreotide at a starting dose of 100 to 150 µg subcutaneous tid or IV (25 to 50 µg/h) if the participant is severely dehydrated, with dose escalation up to 500 µg until diarrhoea is controlled.
 - Administration of antibiotics (e.g., fluoroquinolone).
- Stool work-up (evaluation for blood, faecal leukocytes, *C difficile*, *Salmonella*, *E coli*, *Campylobacter*, and infectious colitis), complete blood count, and electrolyte profile should be performed.
- Continue intervention as described until the participant has been diarrhoea-free for 24 hours.

8.12.3. Management of febrile neutropenia and anaemia

Administer hematologic support as medically indicated (e.g., blood transfusions, granulocyte colony-stimulating factor [G-CSF], erythropoietin, etc.) according to the institutional site standards.

If there are no standard procedures for the use of growth factors, follow Recommendations for the Use of WBC Growth Factors: American Society of Clinical Oncology Clinical Practice

Guideline Update, available at <http://www.instituteforquality.org/practice-guidelines>; or the European Organization for Research and Treatment of Cancer (EORTC) update to 2010 guidelines for the use of G-CSF, available at <https://www.eortc.org/guidelines/>.

8.12.4. Management of Infusion related reactions

There is an inherent risk for IRRs with the administration of mAbs, therefore premedication for prophylaxis of IRRs will be mandatory prior to each dose of futuximab/modotuximab. All participants will be premedicated with standard therapies that include a glucocorticoid and an H1 antagonist. Where indicated, consideration may be given to include an H2 antagonist and/or acetaminophen. Recommended premedication doses are provided ([Section 6.1.2.1](#) and [Appendix 9](#)).

Should a participant experience an IRR while in the study, guidelines for premedication following an IRR are provided ([Section 6.1.2.1.3](#)). Guidelines for the grading and management of IRRs of all severities are also provided ([Section 8.11.2.1](#) and [Appendix 9](#)).

Instructions for the grading and management of IRRs are provided. In all cases the investigator should use best clinical judgment in managing such reactions.

- For Grade 3 reactions, the infusion will be STOPPED. The participant will be either discontinued from treatment or must receive subsequent treatments at a reduced dose and at a prolonged infusion rate.
- For Grade 4 reactions, the infusion will be STOPPED and the participant will be permanently discontinued from treatment.

8.12.4.1. Decrease of infusion rate

For IRRs, the following infusion prolongation instructions are provided:

- For mild IRR (Grade 1), the infusion rate must be decreased by 50% from the prior rate. This lower infusion rate must be maintained in all subsequent infusions.
- For moderate IRR (Grade 2), interrupt the infusion for a minimum of 30 minutes, and at least until there is either amelioration to \leq Grade 1 severity or return to baseline status. Administer supportive care, as medically indicated. Restart the infusion with an infusion rate decreased by 50% from the prior rate. This lower infusion rate must be maintained in all subsequent infusions.
- For Grade 3 reactions, STOP the infusion. Administer supportive care. The participant will be either discontinued from treatment or must receive subsequent treatments at a reduced dose and with a decreased infusion rate (\geq 50% of decrease).
- For Grade 4 reactions, STOP the infusion. Administer supportive care. The participant will be permanently discontinued from treatment.
- All infusion interruptions and subsequent prolongations, including modified infusion times, as well as the toxicity that necessitated them, will be clearly documented on the appropriate page of the participant's e-CRF.

Note: Any assessments to be performed or samples to be collected (e.g., vital signs, PK) at the end of or following the EoI will still be performed or collected beginning at the delayed EoI timepoint.

To enhance participant safety following an infusion prolongation, subsequent infusions will be administered with a lower infusion rate.

8.12.5. Management of dermatologic toxicity

Participants who received futuximab/modotuximab will be monitored weekly for evidence of dermatologic AEs. Dose delay and/or intrapatient dose-reduction(s) will be required upon occurrence of Grade 3 AEs and may be implemented in the event of a Grade 2 dermatologic reaction that is debilitating for the participant.

Recommendations for management of Grade 1 to 3 dermatologic AEs are provided. Participants must be withdrawn from IMP treatment in the event of a Grade 4 dermatologic AE. Guidelines for grading and management of dermatologic AEs and dose reductions to be implemented in the event of such reactions are also provided ([Appendix 10](#)).

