2.4. Rationale for the Study

Acquired resistance to anti-EGFR antibodies in mCRC is caused by both genomic and non-genomic mechanisms. Emergence of clones with mutations in KRAS, NRAS or BRAF are common and confer resistance to anti-EGFR therapies as in the primary resistance setting²⁶. However, a significant portion of patient tumours will remain dependent on the EGFR pathway and second-generation EGFR targeting agents such as futuximab/modotuximab has been designed to address these resistance mechanisms. The Sym004-05 study has evaluated the potential of futuximab/modotuximab to overcome acquired resistance to approved anti-EGFR mAbs in mCRC and has demonstrated encouraging results in a subgroup of molecularly selected patients with KRAS/NRAS and BRAF WT mCRC. To further improve the anti-tumour activity in this patient population the strategy is to combine futuximab/modotuximab with trifluridine/tipiracil. The combination of anti-EGFR antibodies and trifluridine/tipiracil has been explored in several pre-clinical CRC models and demonstrated synergistic or additive activity.^{27,28} Moreover, trifluridine/tipiracil can be safely combined with anti-EGFR therapies with encouraging efficacy, as demonstrated by the APOLLON and the WJOG8916G studies.^{22,23}

Servier plans to develop futuximab/modotuximab (investigational medicinal product [IMP]) in combination with trifluridine/tipiracil to provide a new third-line or later treatment option for patients with KRAS/NRAS and BRAF WT mCRC previously treated with chemotherapy (including oxaliplatin, irinotecan and 5-fluorouracil, anti-VEGF agents) and with anti-EGFR mAb therapy for ≥ 16 weeks, or not considered candidates for available therapies including fluoropyrimidine-, oxaliplatin- and irinotecan-based chemotherapies and anti-VEGF agents. Trifluridine/tipiracil is a standard of care option in that setting and is an approved agent in the EU, US, and Japan.^{7,9,21}

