4.3.1. Products administered

Futuximab/modotuximab and trifluridine/tipiracil are the IMPs. Both will be manufactured by Les LABORATOIRES Servier Industrie (Gidy France). Futuximab/modotuximab is not licenced in any country. Trifluridine/tipiracil is licenced for use in the EU, USA, and Japan.

The labelling of packages complies with the regulatory requirements of each country involved in the study.

Table (4.3.1) 1 provides a description of the IMPs. Additional details on the characteristics of futuximab/modotuximab are provided in the futuximab/modotuximab Investigator Brochure. Additional details on the characteristics of trifluridine/tipiracil are provided in the SmPC.⁸

Table (4.3.1) 1 - Description of the investigational medicinal products

Futuximab/ modotuximab	Pharmaceutical form	Solution for infusion
	Unit dosage	20 mL vial
	Appearance, colour	Clear to opalescent, colourless to slightly yellow solution
	Composition	25 mg/mL active ingredient formulated with histidine as a buffer component, trehalose for tonicity adjustment, polysorbate 20 as stabilizer, and Water for Injection as a solvent, contained within a 20 mL USP Type 1 glass vial with a FluroTec® coated halobutyl/butyl rubber stopper, secured with a cap and flip-off seal.
Trifluridine/ tipiracil 15 mg	Pharmaceutical form	Film-coated tablet
	Unit dosage	15 mg
	Appearance, colour	White round tablet printed with "15" on one side and "102" on the other side
	Composition	15 mg trifluridine and 7.065 mg tipiracil hydrochloride, lactose monohydrate
Trifluridine/ tipiracil 20 mg	Pharmaceutical form	Film coated table
	Unit dosage	20 mg
	Appearance colour	Pale-red round tablet printed with "20" on one side and "102" on the other side
	Composition	20 mg trifluridine and 9.42 mg tipiracil hydrochloride, lactose monohydrate

USP = United States Pharmacopeia

Table (4.3.1) 2 provides a description of the IMP packaging.

Table (4.3.1) 2 - Investigational medicinal product packaging

Futuximab/ modotuximab	Number of units of the pharmaceutical form per primary packaging	1 vial of 500 mg
	Number of primary packaging per secondary packaging	1 vial per small box
Trifluridine/ tipiracil	Number of units of the pharmaceutical form per primary packaging	10 tablets by blister
	Number of primary packaging per secondary packaging	2 blisters

The labelling of packages complies with the regulatory requirements of the country involved in the study.

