8.11. Management of treatment dose adaptations due to toxicities

For participants who have experienced a dosing modification, reasons for dose modifications or delays, the supportive measures taken, and the outcome will be documented in the participant's source documents and recorded in the e-CRF.

In the futuximab/modotuximab plus trifluridine/tipiracil arm doses of either futuximab/modotuximab, or trifluridine/tipiracil, or both drugs can be modified, depending on the toxicity observed.

General rules:

Before starting a new treatment cycle, toxicity must have resolved as specified in the [Sections 8.11.1](#) and [8.11.2](#) and the safety criteria to be met as specified in the [Section 6.1.5](#).

- If toxicity due to any of the IMPs does not resolve during the given cycle to Grade 1 or baseline, the start of the next cycle will be delayed for a maximum of 30 days for trifluridine/tipiracil and 21 days for futuximab/modotuximab (see [Sections 8.11.1](#) and [8.11.2](#)). If more than the maximum delay period is needed for recovery, the next cycle should be started with the IMP not concerned by the toxicity.
- If, in the opinion of the investigator, the toxicity is clearly related to one of the treatments, reduction of one and not the other agent is appropriate. If, in the opinion of the investigator, the toxicity is related to the futuximab/modotuximab only futuximab/modotuximab should be reduced according to recommended dose modifications. If, in the opinion of the investigator, the toxicity is related to the trifluridine/tipiracil only trifluridine/tipiracil should

be reduced according to recommended dose modifications. If the toxicity is related to the combination of two agents, both agents should be reduced (if applicable), interrupted or discontinued according to the recommended dose modifications.

- Participants may have trifluridine/tipiracil discontinued and continue on futuximab/modotuximab alone. Similarly, participants may discontinue futuximab/modotuximab and continue on trifluridine/tipiracil alone if appropriate.

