8.11.2.2. Dose Delay

Toxicities may be managed by delay in dosing, provided they do not meet the criteria for IMP discontinuation ([Section 5.8.1](#)). In such cases, the period between any 2 scheduled doses may be extended up to 3 days (inclusive) to allow an improvement of the toxicity. Such delays will be considered an extension within the current cycle. If a delay of more than 3 days from the scheduled dose date is necessary, the dose should be omitted and proceed to the next scheduled dose (i.e. 14 days from the last dose).

If 3 consecutive doses are needed to be omitted (i.e. more than 21 days from the last dose of futuximab/modotuximab), the participant should be discontinued from futuximab/modotuximab. All delays of futuximab/modotuximab must be documented on the appropriate page of the participant's e-CRF.

If toxicity does not resolve during the given cycle to Grade 1 or baseline, the start of the next cycle may be delayed by a maximum of 21 days from the last dose of futuximab/modotuximab administered to allow the initiation of both IMPs at the same time in the next cycle. If more than 21 days from the last dose administered are needed for recovery, futuximab/modotuximab should be discontinued and the next cycle will start with only trifluridine/tipiracil.

Dosing may be restarted at the same dose, as clinically indicated. However, administration of futuximab/modotuximab may only be restarted provided retreatment criteria are met ([Section 6.1.5](#)).

For treatment restart with no dose reduction:

- If treatment restart after the omission of 1 dose (i.e. treatment delay up to 14 days from the last dose), it is recommended that dosing restart with maintenance dose of 6 mg/kg;
- If treatment restart after the omission of 2 consecutive doses (i.e. treatment delay up to 21 days from the last dose), it is recommended that dosing re-start with the re-administration of a loading dose of 9 mg/kg followed by weekly maintenance doses of 6 mg/kg.

For treatment restart with dose reduction, see Section 8.11.2.3.

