Appendix 10: Management of Dermatologic Adverse Events

A. Grading and Management of futuximab/modotuximab-Related Dermatologic AEs

Recommendations for management of Grade 1 to Grade 3 futuximab/modotuximab-induced dermatologic AEs (*i.e.*, rash, xerosis, paronychia, pruritus, photosensitivity, and fissures) are summarized below. If a patient experiences any Grade 4 dermatologic AE, the patient must be withdrawn from futuximab/modotuximab treatment. It is strongly recommended that a dermatologist is consulted in the event of Grade 3 or Grade 4 dermatologic AE.

Futuximab/modotuximab - Management of Rash			
NCI-CTCAE Grade	Action with futuximab/modotuximab	Treatment- Rash	
1	Papules and/or pustules covering < 10% body surface area (BSA) , which may or may not be associated with symptoms of pruritus or tenderness	Continue at the same dose	Topical : Face and Chest Steroid creams of low potency; alclometasone 0.05% or desonide 0.05% or fluocinolone 0.01%; 2 x daily Topical : Rest-of-body moisturizers; 2 x daily Systemic ¹ : minocycline 100 mg/day or doxycycline 200 mg/day; for at least 4 weeks
2	Papules and/or pustules covering 10-30% BSA , which may or may not be associated with symptoms of pruritus or tenderness; associated with psychosocial impact; limiting instrumental activities of daily living (ADL); papules and/or pustules covering > 30% BSA with or without mild symptoms	Continue at the same dose If locally debilitating for the patient, consider following guidelines for dose-delay and dose reduction as outlined in the Dose Reduction for Grade 3 Dermatologic AEs table in Section B below	Topical : See Grade 1 Systemic ¹ : 
 - minocycline 100 mg/day or doxycycline 200 mg/day; for at least 4 weeks - 1 week course of oral steroid: methylprednisolone 4 mg tablets: 
 • Day 1: 2-1-1-2 • Day 2: 1-1-1-2 • Day 3: 1-1-1-1 • Day 4: 1-1-1 • Day 5: 1-0-1 • Day 6: 1
3	Papules and/or pustules covering > 30% BSA , with moderate or severe symptoms; limiting selfcare ADL; IV antibiotics indicated	Delay dose of futuximab/modotuximab, continue skin treatment and re-assess. Refer to the Dose Reduction for Grade 3 Dermatologic AEs table in Section B below for further guidelines on dose reduction	Topical : See Grade 1 Systemic ¹ : See Grade 2

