Abbreviations (in alphabetical order): AE, adverse event; kg, kilogram; mg, milligram
Note: Dose reductions for 9 mg/kg loading not applicable. For dose delays, re-assess after < 2 weeks. Longer delays are allowed if no recovery to < Grade 2 after 2 weeks

In each case, the next treatment should be delayed, and the patient's condition should be reassessed after 1 week, and if necessary, 2 weeks. Treatment should be delayed further if the AE remains at Grade 3 after 2 weeks.

In the case of a Grade 2 dermatologic AE which is locally debilitating for the patient, the guidelines outlined above may be followed at the investigator's discretion.

Participants must be withdrawn from futuximab/modotuximab treatment in the event of a Grade 4 dermatologic AE.

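### After a Grade 4 dermatologic event, Section 8.12.5 read literally stops both study drugs, while the Appendix 10 it cites stops only futuximab/modotuximab

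*Protocol*

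**What the plan says.** The Grade 4 dermatologic rule appears in three places in the protocol.

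- Section 8.12.5: "Participants must be withdrawn from IMP treatment in the event of a Grade 4 dermatologic AE".
- Appendix 10, part A: "If a patient experiences any Grade 4 dermatologic AE, the patient must be withdrawn from futuximab/modotuximab treatment".
- Appendix 10, part B: "Participants must be withdrawn from futuximab/modotuximab treatment in the event of a Grade 4 dermatologic AE".

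Section 8.12.5 sends the reader to Appendix 10 for grading, management and dose reduction of these events. The meaning of IMP is fixed in Section 4.3.1: "Futuximab/modotuximab and trifluridine/tipiracil are the IMPs".

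The general dose-adaptation rules treat the two drugs separately. Section 8.11 says that "participants may discontinue futuximab/modotuximab and continue on trifluridine/tipiracil alone if appropriate". Section 8.11.2.2, on antibody toxicity that takes too long to resolve, says that "futuximab/modotuximab should be discontinued and the next cycle will start with only trifluridine/tipiracil".

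**The concern.** This is a mandatory safety rule, and its scope depends on which page is read. A site that combines 8.12.5 with the 4.3.1 definition takes the participant off both drugs. A site that follows Appendix 10 stops the antibody and may continue trifluridine/tipiracil. On the literal reading, a participant loses study supply of the backbone drug because of a toxicity that the protocol associates with the antibody: Section 2.8 says dermatological toxicity is not commonly reported with trifluridine/tipiracil alone.

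The split would also show in the safety reporting that remains. SAP Section 3.5.1 describes treatment-emergent events leading to withdrawal separately for each drug. SAP Section 5.2.1.2 has a deviation category for participants who met a withdrawal criterion but were not withdrawn, so a site correctly following Appendix 10 could be queried under a literal 8.12.5.

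**Working it through.** There is no figure to recompute; the check is a comparison of texts.

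**1. Count the statements of the rule.** There are three: 8.12.5, Appendix 10 A and Appendix 10 B. One of the three says IMP, and two of the three name futuximab/modotuximab. The sentences in 8.12.5 and Appendix 10 B match word for word except for that noun.

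**2. Is the literal reading open to a site?** Yes. Section 4.3.1 covers both drugs. Text near the stopping rules also uses the term for either one. The DLT definition in 4.1.3.2 explains the IMPs as one drug, the other, or both. Section 8.11.1 refers to both IMPs starting together. Section 8.11 says that, once the maximum delay is exceeded, "the next cycle should be started with the IMP not concerned by the toxicity", which makes sense only if each drug is an IMP.

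**3. Is the literal reading consistent with the other dose rules?** No.

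| Situation | Antibody | Trifluridine/tipiracil |
|---|---|---|
| Grade 4 dermatologic event, 8.12.5 with 4.3.1 | stop | stop |
| Grade 4 dermatologic event, Appendix 10 | stop | not mentioned, so 8.11 applies |
| Antibody toxicity needing more than 21 days from the last dose, 8.11.2.2 | stop | continue |
| Grade 3 or 4 non-haematologic reaction to trifluridine/tipiracil, Table (8.11.1) 3 | not addressed | wait for Grade 1 or baseline, resume 5 mg/m² lower (table's exceptions aside) |

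Read literally, 8.12.5 is harder on trifluridine/tipiracil for a skin event attributed to the other drug than Table (8.11.1) 3 is for that drug's own Grade 4 non-haematologic reaction.

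**4. Which rule was probably meant?** Appendix 10. Section 8.12.5 opens with participants who received the antibody and closes by citing that appendix, and 8.11.2.3 sends readers there for dermatologic dose reductions. The protocol also uses IMP loosely elsewhere: Section 2.4 labels the antibody alone that way ("futuximab/modotuximab (investigational medicinal product [IMP]) in combination with trifluridine/tipiracil"). For Grade 4 infusion reactions, Section 6.1.2.1.3 bars further futuximab/modotuximab, while Appendix 9 states the same bar using IMP.

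**5. How far apart are the two readings in practice?** Less than the wording suggests. Under Appendix 10, trifluridine/tipiracil would still wait for the retreatment criteria in 6.1.5 before a new cycle. In the Lead-In, a Cycle 1 Grade 4 skin toxicity that meets the DLT definition already delays the study treatments (4.1.3.2 and 4.1.3.3). Under 8.12.5, Section 6.5 leaves later treatment to the physician, so trifluridine/tipiracil outside the study remains possible.

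**The case against.** The strongest reply is that this is loose wording which the document resolves for itself. The sentence recurs in the cited appendix with the drug named, the infusion-reaction rule shows the same swap of nouns, and 8.11 already ties action to the responsible agent. Divergent handling by sites is a possibility, not something shown. A Grade 4 event is life-threatening and so serious, which means the sponsor hears of it within 24 hours, and treatment discontinuation must also be notified immediately; a misreading would surface quickly. The literal reading is also the more cautious one after a life-threatening event. Finally, the event need not be due to the antibody: 8.11 calls for action on both agents if the toxicity comes from the combination.

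Most of this stands, and it limits the weight of the point. It shows which rule was intended and that the consequence is modest. It does not repair the operative sentence. A mandatory withdrawal rule should not require the reader to set aside the protocol's own definition, particularly when neighbouring sections use IMP for either drug. The attribution point bears on the correction, which should defer to 8.11 and not promise continuation in every case.

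**Conclusion.** The concern holds: Section 8.12.5 is wrong as written, at low severity. Taken with Section 4.3.1 it withdraws both drugs, whereas the appendix it relies on withdraws one.

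The number affected is limited to participants on futuximab/modotuximab who have a Grade 4 dermatologic event. The documents give no Grade 4 dermatologic rate for the antibody alone or for the combination, so neither an estimate nor an upper bound is offered. The SAP introduction records that the Randomised part was cancelled, and nothing here alters sample size, power, type I error or the survival analysis.

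The conclusion that Appendix 10 is the intended rule is an inference from its two explicit statements, the cross-reference to it and the structure of 8.11. The sponsor should confirm it.

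**What to change.** In Section 8.12.5, replace the reference to IMP treatment with futuximab/modotuximab treatment. Add that trifluridine/tipiracil may continue under Section 8.11 once the retreatment criteria in Section 6.1.5 are met. Deferring to 8.11 keeps its attribution and combination-toxicity rules in force, so toxicity judged to come from both agents would still lead to action on both.

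All three statements of the rule would then agree. The cost is one sentence in one amendment, with no added procedures or participants.
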